#### **IV. BIOSTATISTICAL ANALYSIS**

Data forms and questionnaires will be coded in a standardized manner, and double-entered into our database. Digital measures/recordings will be similarly tracked in our database and regularly backed up. Analyses will be conducted using standard statistical software such as SAS and Matlab.

Sample size calculations and data analysis:

*Aim 1:*

For planning sample size calculation for this study, we considered the surrogate pain outcomes as the main outcome for such analysis; considering the two studies showing significant alterations of these outcomes in NSCLBP [118], an effect in the active tDCS in conjunction with active TUS that is twice of the effect in SHAM tDCS in conjunction with SHAM TUS would be adequate. Considering this effect size and a power of 80% and alpha of 5%, we would need 6 subjects per group for a total of 12 subjects. Therefore considering dropouts and also to increase the sample in phase I for the clinical outcome, we increased the sample to 20 subjects (10 for each arm), that would also give a power to detect significant differences of 2 points in VAS between the 2 groups; though the clinical outcome is not the main outcome in phase 1. For Phase 2, we doubled the sample size as to have enough power to detect a difference of 1.3 in VAS between the two groups that would therefore be adequate to demonstrate a clinically meaningful difference between the two groups. We considered differences smaller than that not clinically meaningful.

All analyses will be conducted according to the principle of intention-to-treat (using regression-based single imputation method). We will also perform an additional sensitivity analysis in

which we will use the method of last observation carried forward. The primary outcome will be TS and CPM [118] (in phase 1) and VAS (in phase 2) changes as indexed by VAS scores, biomechanical function changes as indexed with the motion analysis suite, and global self-assessment changes. Differences between the two groups (active tDCS in conjunction with active TUS and SHAM tDCS in conjunction with SHAM TUS) will be tested using Student's t-test and, in addition, we will adjust for important baseline variables and also test the time effect in general mixed longitudinal models. This model will be used for the primary and secondary outcomes. Secondary analyses will be conducted in an exploratory manner (no correction for multiple comparisons). Similar analysis will be conducted for the adverse effects measuring continuous outcome and for the categorical outcomes we will use Fisher's exact test. In both cases, for safety analysis we will use uncorrected p-value to increase the likelihood of detecting detrimental adverse effects.

332-6.

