## **II. SUBJECT SELECTION**

In phase II, we will recruit about 80 subjects in order to randomize 40 patients with NSCLBP for this study. Subjects will need to meet all of the following inclusion criteria and none of the following exclusion criteria:

Inclusion Criteria:

1. Providing informed consent to participate in the study
2. 18 to 85 years old
3. Having non-specific chronic low back pain as defined by [6, 7] (existing pain for at least 3 months and having pain on at least half the days in the past 6 months) with an average of at least 3 on a 0-10 VAS scale
4. Pain resistant (partial or no response) to common analgesics and medications for chronic pain such as Tylenol, Aspirin, Ibuprofen, Soma, Parafon Forte DCS, Zanaflex, and Codeine
5. Must have the ability to feel sensation by Von-Frey fiber on the forearm

Exclusion Criteria:

1. Subject is pregnant
2. Contraindications to tDCS in conjunction with TUS:
  - a. Metallic implant in the brain
  - b. Implanted brain medical devices
3. History of alcohol or drug abuse within the past 6 months as self reported
4. Use of carbamazepine within the past 6 months as self reported
5. Suffering from severe depression (with a score of >30 in the Beck Depression Inventory)
6. History of neurological disorders as self reported (including epilepsy (note patients will also be evaluated via EEG at baseline and any patient showing abnormal EEG activity will be removed))
7. History of unexplained fainting spells as self reported
8. History of severe head injury resulting in more than a momentary loss of consciousness as self reported
9. History of neurosurgery as self reported
10. Unstable pain (defined as a difference in pain intensities larger than 4 points on a 0-10 VAS scale between the average over the week prior to visit 2 and the average over the week prior to visit 4a [96])
11. Large placebo responder: having a reduction of pain greater than 72.52% (VAS pain now post stimulation on V3 compared with VAS pain now pre stimulation on V2) or VAS now of 0 or 1 following any stimulation during Run-in period.
12. Low Adherence during the Run-in stimulation visits (ie. not attending both Run-in stimulation visits within approximately one week)
13. Low baseline pain: VAS pain weighted average < 3 prior to randomization during visit 4a

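### Can 20 patients per arm detect a 1.3-point VAS difference when the plan gives no standard deviation?

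*Combined protocol and SAP*

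**What the plan says.** The sample size text is in Section IV (Biostatistical Analysis), Aim 1. It starts from the surrogate pain outcomes: "Considering this effect size and a power of 80% and alpha of 5"%, 6 subjects per group are needed. The total then rises to 20 ("Therefore considering dropouts and also to increase the sample in phase I for the clinical outcome"), which is said to "give a power to detect significant differences of 2 points in VAS between the 2 groups". For Phase II, "we doubled the sample size as to have enough power to detect a difference of 1.3 in VAS between the two groups", followed by "We considered differences smaller than that not clinically meaningful". Section III gives 20 per arm and ends enrolment once 40 have entered the randomised part.

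The primary outcome is given as "VAS (in phase 2) changes as indexed by VAS scores". Groups are to be "tested using Student's t-test and, in addition, we will adjust for important baseline variables" in longitudinal mixed models, and the model is to serve both primary and secondary outcomes. Analysis is by intention to treat with regression-based single imputation, and last observation carried forward is a sensitivity analysis.

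The text gives no SD for VAS or its change, no power figure for VAS, no sidedness, no Phase II dropout rate and no primary visit. Section II uses more than one form of VAS, but for eligibility: a current rating ("VAS pain now post stimulation on V3 compared with VAS pain now pre stimulation on V2"), an average over a week, and a weighted average.

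**The concern.** A detectable difference means something only beside an SD and a power. Here the 80% and 5% are attached to the surrogate calculation, and the remark about dropouts to Phase I. The Phase II figure is presented simply as a doubling.

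The endpoint is also loose. VAS is listed 35 times after randomisation: once at Visit 4b, twice at each of Visits 5 to 19 (15 x 2 = 30), and once at each of Visits 20 to 23 (4). A momentary rating and a weekly average have different SDs.

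The plan treats 1.3 points as its limit of clinical relevance. If the true SD were well above what the design tolerates, a non-significant result might be read as absence of a meaningful effect when the trial had little chance of finding one.

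**Working it through.** **Inputs.** Difference 1.3 and 20 per arm (Sections IV and III); 2 points and 10 per arm for Phase I (Section IV). Alpha 5% and power 80% are stated for the surrogate outcome; carrying them over to VAS is an assumption, as is two-sidedness.

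**Method.** Two-sample t-test with n per arm, 2n − 2 degrees of freedom and noncentrality δ / (σ√(2/n)). Solving for 80% power gives the required standardised difference d = δ/σ:

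- n = 9: d = 1.407
- n = 10: d = 1.325
- n = 20: d = 0.909

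**Step 1: the largest SD that supports 1.3.** σ = 1.3 / 0.909 = 1.43. The same calculation one-sided gives 1.62; two-sided with 90% power it gives 1.24.

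**Step 2: the SD implied by the plan's Phase I figure.** The Phase II figure cannot be reproduced directly, but it can be set against the Phase I statement.

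- All 10 per arm analysed: σ = 2 / 1.325 = 1.51. With 20 per arm the detectable difference is 0.909 x 1.51 = 1.37, and power at 1.3 is 76%.
- One dropout per arm in Phase I, so 9 analysed: σ = 2 / 1.407 = 1.42. With 20 per arm the detectable difference is 0.909 x 1.42 = 1.29, and power at 1.3 is 80.5%.
- In reverse, an SD of 1.43 makes the Phase I detectable difference 1.325 x 1.43 = 1.89, which rounds to 2. At that SD, power for exactly 2 points with 10 per arm is 84%.

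So 2 points and 1.3 points fit together under ordinary rounding or a small Phase I dropout allowance. On the least favourable of these readings, power is about 4 percentage points below 80%.

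**Step 3: sensitivity to the SD** (two-sided, 20 per arm).

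| SD | Basis | Power at 1.3 | Detectable at 80% power |
|---|---|---|---|
| 1.25 | assumed | 89% | 1.14 |
| 1.42 | Phase I, 9 analysed per arm | 80.5% | 1.29 |
| 1.43 | ceiling | 80% | 1.30 |
| 1.51 | Phase I, 10 analysed per arm | 76% | 1.37 |
| 1.75 | assumed | 63% | 1.59 |
| 2.0 | assumed | 52% | 1.82 |
| 2.5 | assumed | 36% | 2.27 |

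Only the rows at 1.42 and 1.51 come from the plan's own statements.

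**Step 4: the adjusted model.** To bring a residual SD of 1.51 down to 1.43, baseline variables must explain 1 − (1.43/1.51)² = 0.10 of the variance of the VAS change, a correlation of about √0.10 = 0.32. The plan gives no correlation, so this shows only how little adjustment would close the gap.

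**Step 5: dropout.** With 18 or 16 per arm (assumed 10% or 20% loss) the ceiling becomes 1.3 / 0.961 = 1.35 or 1.3 / 1.024 = 1.27. These are completers' figures. The plan instead imputes and analyses 20 per arm.

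**The case for a change.** The strongest case for a change is that the plan does more than omit an SD. It asserts adequacy for a named difference and calls anything smaller not meaningful, so readers will use 1.3 to interpret a null result. At an assumed SD of 2.0 a true 1.3-point effect would be missed about half the time. The remedy is one paragraph. Single imputation fills empty cells without restoring lost information, so dropout still costs power. And with no primary visit, no one can say which SD applies.

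Much of this is true. The inputs are absent, imputation does not recover information, and the t-test ceiling leaves little margin. But three things weaken it as grounds for a change.

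- The low-power rows need SDs that nothing in the plan supports. The run-in also removes patients with unstable pain, large placebo responses or low baseline pain. Its effect on the SD of change is not quantified, so an SD for an unselected population cannot simply be assumed.
- Reading a null result does not rest on the planning SD. Once the data are in, the observed SD and the confidence interval for the difference show whether 1.3 points is excluded.
- The VAS measure is less open than it looks. The week-average and weighted forms appear in the eligibility rules, while the Description of Assessments presents VAS as the rating taken when patients attend sessions, with the diary covering pain away from the laboratory. The missing visit is a question of endpoint definition; naming it would not show that 40 patients are too few.

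**Conclusion.** The concern is right that the 1.3-point claim cannot be checked from the public text, and right in its arithmetic: 20 per arm needs an SD of 1.43 or less for 80% power with a two-sided 5% t-test. It does not show that the claim is wrong. If the Phase I statement also meant 80% power, the plan's own figures give an SD of about 1.42 to 1.51 and power of about 76% to just over 80%. That agrees with the claim or falls slightly short of it, before any gain from baseline adjustment.

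What remains is missing detail. Filling it in means recording inputs the sponsor presumably had; the text mentions a research strategy that is not part of the public document. Enrolment, allocation and analysis would be unchanged, and the stated difference would move only if an unknown SD proved to be above the ceiling. No change to the plan follows.

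This rests on carrying 80% power and two-sided 5% over to VAS, and on 20 analysed per arm as the intention-to-treat rule provides. A documented SD well above 1.5 for the VAS change would alter the conclusion.

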### **III. STUDY PROCEDURES**

Because our protocol involves a run-in phase (Part I), we expect that up to 90 patients may enter the run-in phase so we will be able to randomize 40 eligible subjects to participate in this study (in phase II). When the target number of 40 subjects (for phase II) entering the randomized phase

(Part II) is completed, enrollment will end. Subjects who passed the run-in phase (Part I) successfully will then be randomly assigned to receive treatment in Part II with active tDCS+active TUS (n=20) or sham tDCS+sham TUS (n=20 inactive transducers).

**General Study Outline:** This two-Part study will consist of 23 visits over the course of about 15 weeks. After Visit 1, the remaining Part I of the study will take about a week (Visits 2-4a). Prior to any assessments, the subject will consent to participate in both Part I and Part II, pending that the subject fits the additional eligibility criteria\* of the run-in period. After completion of Part I, eligible subjects will continue onto Part II, the main interventional portion of the trial. Part II of the study will take place over the remaining weeks (Visits 4b-23).

*Part I Study Flow – Run-in Period (Visits 1-4a):*

- Screening Visit
- Run-in Visit 2&3 – sham stimulation visits
- Rescreening Visit

*Part II Study Flow – (Visits 4b-23):*

- 10 sessions of tDCS stimulation over 2 weeks
- Bi-weekly sessions of tDCS stimulation over 3 weeks
- 4 Follow-Up Visits – 2 week, 4 weeks, 6 weeks, and 8 weeks post-stimulation

Eligibility criteria for Part II include:

- VAS pain score greater than 1 following either of the two SHAM stimulation sessions [97] during Part I and pain reduction not greater than 72.52% (i.e. not a large placebo response)
- Stable pain intensities (defined as a difference in pain intensities less than or equal to 4 (on a 0-10 VAS scale) between the average over the week prior to visit 2 and the average over the week prior to visit 4a [96])
- High adherence during the Run-in stimulation visits (defined as completing both Run-in stimulation visits within approximately one week)
- VAS pain weighted average  $\geq 3$  prior to randomization during visit 4a (i.e. not exhibiting low baseline pain)

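### Does power for a 1.3-point VAS difference lead the plan to call a smaller significant difference clinically meaningful?

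*Combined protocol and SAP*

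**What the plan says.** Section III, Study Procedures, sets the arms at "active tDCS+active TUS (n=20) or sham tDCS+sham TUS (n=20 inactive transducers").

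Section IV, Biostatistical Analysis, under the sample size heading for Aim 1, starts from the Phase 1 surrogate pain outcomes: "Considering this effect size and a power of 80% and alpha of 5%, we would need 6 subjects per group". It then raises Phase 1 to 10 per arm, "that would also give a power to detect significant differences of 2 points in VAS between the 2 groups". For Phase 2 the sample is doubled, to give the trial enough power to "detect a difference of 1.3 in VAS between the two groups that would therefore be adequate to demonstrate a clinically meaningful difference", and the paragraph closes with "We considered differences smaller than that not clinically meaningful".

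The analysis text further on in section IV says that group differences "will be tested using Student's t-test and, in addition, we will adjust for important baseline variables" and test the time effect in mixed longitudinal models. It gives no separate criterion for clinical relevance. For VAS, the plan states no SD, no numerical power and no sidedness.

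**The concern.** The sample size paragraph moves from power to detect 1.3 points to being able to demonstrate a clinically meaningful difference, with a 'therefore' between them. Read literally, that treats p<0.05 as proof of at least 1.3 points. A test against zero gives no such proof: it can reject at an observed difference well under 1.3, and the analysis text never mentions 1.3 again.

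If the plan really worked that way, the trial's main clinical claim would be at stake. A significant difference of about 1 point could be published as clinically meaningful although the same paragraph puts such a difference below relevance. Baseline adjustment would not help, because any gain in precision moves the significance boundary lower still.

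**Working it through.** **Inputs.** Target difference 1.3 points and 20 per arm (sections IV and III). Student's t-test, so 20 + 20 − 2 = 38 df. Power 80% and alpha 5% are stated for the Phase 1 surrogate outcome and are carried over to VAS as an assumption. Two-sided testing is also assumed.

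**Can the plan's own figure be rebuilt?** Not directly, because no SD is given for VAS. Solving backwards, critical t = 2.0244 and the noncentrality for 80% power is 2.875, so

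SD = 1.3 / (2.875 × √(2/20)) = 1.43, with standard error 1.43 × √(2/20) = 0.452.

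The Phase 1 statement (2 points, 10 per arm, 80% power) implies SD = 2 / 1.325 = 1.51. With that SD, 20 per arm gives 76% power for 1.3 points, or 80% power for 1.37. The two statements agree about as well as rounding allows. No figure is shown to be miscalculated.

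**Where does the test become significant?**

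Boundary = target × (critical t / noncentrality) = 1.3 × 2.0244 / 2.875 = 0.915.

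The SD cancels once the power is fixed. Other settings at 20 per arm:

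| Power for 1.3 | Two-sided 5% | One-sided 5% |
|---|---|---|
| 70% | 1.03 | 0.99 |
| 80% | 0.92 | 0.87 |
| 90% | 0.79 | 0.74 |

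With the Phase 1 SD of 1.51 the two-sided boundary is 2.0244 × 1.509 × 0.3162 = 0.97.

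**Is this peculiar to this trial?** No. The ratio 2.0244 / 2.875 = 0.70 depends only on alpha, power and, slightly, the degrees of freedom. The Phase 1 pair behaves the same way: 2 points at 10 per arm gives a boundary of 1.42, and 1.42 / 2 = 0.71. To bring the boundary up to the target, the SD would have to be 1.3 / (2.0244 × √(2/20)) = 2.03, and power for 1.3 would then be only about 50%. A superiority test that cannot reject below its target therefore has only about even odds of rejecting when the target is true.

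**What are the operating characteristics?** With SD 1.43:

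| True difference | Significant | Significant, estimate < 1.3 | Significant, estimate ≥ 1.3 |
|---|---|---|---|
| 0.9 | 49% | 30% | 19% |
| 1.3 | 80% | 30% | 50% |

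So significant estimates below 1.3 will be common. Whether that does harm depends on what the plan says about them.

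**What does the plan say about them?** Set the two sentences side by side. The first concerns the adequacy of the sample; what it calls adequate is having "enough power to detect a difference of 1.3 in VAS between the two groups". The second fixes how differences below 1.3 are regarded. A significant estimate of, say, 1.0 is then a difference from sham that is smaller than the plan regards as clinically meaningful. Neither the sample size paragraph nor the analysis text says that p<0.05 alone establishes clinical relevance. The feared report would need such a rule, and it would contradict the sentence that follows the disputed clause.

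**The case for a change.** The best case for the concern is that the plan names 1.3 as its threshold, uses the word 'demonstrate', and then never ties 1.3 to the estimate or its confidence interval. An observed 0.92 would be significant with a 95% CI from 0.005 to 1.84, and nothing in section IV spells out how to describe that result. A rule set before unblinding would remove any later choice.

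Part of this stands. 'Powered to detect a true difference of 1.3' would be more exact wording, and the SD, power and sidedness for VAS are not given. These are matters of wording and missing detail. They do not show that the plan reaches a wrong conclusion.

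Nor is there one obvious rule that the plan has failed to adopt. The natural candidate is to declare a clinically meaningful difference when p<0.05 and the estimate is at least 1.3. It would make that declaration in 19% of trials if the true difference were 0.9, and in 41% if it were 1.2, both below the threshold. It reads a point estimate as proof of the true value, which is the same kind of inference the concern objects to: an estimate of exactly 1.3 has a 95% CI of 0.38 to 2.22. The strict alternative, a lower 95% limit of at least 1.3, needs a true difference of 1.3 + 2.875 × 0.452 = 2.60 points for 80% power at 20 per arm. Choosing between these is a trade-off on which statisticians can reasonably differ.

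**Conclusion.** The concern does not hold. Its arithmetic is right: under two-sided 5% and 80% power, the t-test is significant from about 0.92 points, and if the true difference is 1.3, some 30% of trials would be significant with an estimate below 1.3. These figures describe ordinary superiority testing and leave the sample size, the test and the error rates intact.

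The harm would require a rule that equates significance with clinical relevance. Section IV contains no such rule, and its own threshold sentence points the other way. This conclusion rests on reading the disputed clause as part of the sample size justification, where it stands, together with the sentence that follows it. It does not depend on the exact boundary: for any power above about 50% the boundary lies below 1.3, and the plan's label for an estimate under 1.3 is the same throughout.

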### **Visit 4a**

Rescreening Visit – (Approx Time: 1 ¼ hours)

*This study will be scheduled ~1 week after the first baseline measurements were done.*

The subject will complete a series of assessments:

- Urine pregnancy exam (if applicable)
- Visual Analog Mood Scale (VAMS)
- Mini Mental State Examination (MMSE)
- Stroop test
- Neurological and Physical Exam
- Visual Analogue Scale (VAS) for Pain
- Pain/Medication Diary
- Quantitative Sensory Testing (QST)
- Walking Test
- Postural Stability/Standing Test
- One Leg Stance Test
- Trunk Mobility Test
- Screening form for part II\*

\* If the subject is eligible for part II, then they will complete visit 4b in the same day.

Note, patients who exhibit large placebo effects (defined as exhibiting VAS=0 or VAS=1) following either of the two SHAM stimulation sessions[97] during Part I and score reduction higher than 72.52%; unstable pain intensities (defined as a difference in pain intensities larger than 4 (on a 0-10 VAS scale) between the average over the week prior to visit 2 and the average over the week prior to visit 4 [96]), low baseline pain (defined as weighted VAS avg < 3) prior to randomization during visit 4) or who are not compliant with the Run-In protocol (defined as not completing both Run-in stimulation visits within approximately one week) will be excluded from the full trial [96-98], and thus will not receive MRIs and will not come for

additional visits. By following this Run-in strategy, we will maximize trial resources by excluding patients who demonstrate poor compliance and are less likely to complete the trial. More importantly, we will increase the likelihood that the effects we are measuring in the full trial are biological in nature and directly caused by the stimulation intervention [97, 98]. Note, a patient can be screened out in any of the visits prior to Visit 4b.

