#### *Blinding:*

All subjects and investigators will be blinded to the group assignment except for the co-investigators providing stimulation and staff involved in the randomization process (the latter would otherwise not be involved in study procedures). Only the staff involved in the randomization will be authorized to break the blind if there is a clinical need as requested by the PI, clinical care providers, Medical Monitor, or IMC. The patients will remain blinded until they have completed all visits (whether they complete all 23 visits or drop out early), or in the case of an adverse event necessitating un-blinding.

If the subject receives sham stimulation during Part II, he/she may re-enroll into an open label portion of the study, where he/she will receive 10 days of active tDCS/TUS. Un-blinded co-investigators (e.g., who provided stimulation) will coordinate with subjects electing to enter into the open label phase, which will be conducted by the un-blinded study staff. In the open label phase, we will complete the VAS assessments on Day 5 and Day 10 of stimulation. This

collected data will not be analyzed with the main data collected in the study. This data will be used for exploratory analyses only.

After stimulation subjects will complete the following assessments:

- Visual Analog Mood Scale (VAMS)
- Mini Mental State Examination (MMSE)
- Stroop test
- Neurological and Physical Exam
- EEG recording \*
- Adverse Events (AE)
- Visual Analogue Scale (VAS) for Pain

\* *The EEG can be performed at anytime during the first week of stim (V4b-V8).*

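### Once VAS values are missing, regression-based single imputation followed by a t-test understates the standard error if arm is in the imputation model, or biases the effect toward zero by a predictor-dependent amount if it is not

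*Combined protocol and SAP*

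**What the plan says.** In section IV, under Aim 1, the missing-data rule is: "All analyses will be conducted according to the principle of intention-to-treat (using regression-based single imputation method"). A sensitivity analysis is added in "which we will use the method of last observation carried forward". The arms are compared by Student's t-test; "in addition, we will adjust for important baseline variables and also test the time effect in general mixed longitudinal models". The section does not state the imputation predictors, whether arm is among them, whether a random residual is added, or how the standard error and degrees of freedom allow for imputed values.

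Phase 2 is sized for a VAS difference of 1.3 with 20 per arm, and the section adds: "We considered differences smaller than that not clinically meaningful".

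On losses, the Blinding section foresees subjects leaving ("whether they complete all 23 visits or drop out early"). Section III closes recruitment once 40 subjects are in the randomized part ("Part II) is completed, enrollment will end"), so a lost subject is not replaced. No phase 2 dropout rate or allowance is given.

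**The concern.** A regression-imputed value is a function of the observed subjects' data. A t-test on the completed data set counts it as an independent measurement.

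- **Arm in the imputation model.** The estimate is unbiased if data are missing completely at random. However, the within-arm spread is understated when no residual is added, and the sample size is overstated in either case. Nothing in the reported p-value or interval shows this.
- **Arm left out.** Imputed values in both arms are drawn toward a common regression line, so the estimated difference shrinks. The test keeps its type I error but loses effect and power.

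As written, the plan allows either, and with 20 per arm each lost subject is 5% of an arm. Read literally, the words covering all analyses also put the mixed models on imputed data, although the text does not say outright that they are fitted to imputed values.

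**Working it through.** **Inputs from the documents.** 20 per arm; difference 1.3; alpha 5%; Student's t-test; single imputation by regression. Power of 80% is stated only for the 6-per-group surrogate calculation and is assumed here for phase 2. No SD is given.

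**Assumptions not in the documents.** Values missing completely at random, with equal loss per arm; two-sided t-test on change; baseline–outcome correlation 0.3–0.7; earlier-VAS-to-outcome correlation 0.7–0.9; 5% or 10% missing (1 or 2 of 20 per arm).

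**Step 1, the plan's own figure.** By the normal approximation, 1.3 points with 20 per arm has 80% power if SD = 1.3 / [(1.960 + 0.842) × √(2/20)] = 1.3 / 0.886 ≈ 1.47. Without a stated SD, the sample size can be neither confirmed nor refuted. This SD only sets the scale for power below.

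**Step 2, hand check with arm included.** Take the limiting case where the predictors carry no information on change, so each of m missing values per arm is filled with its arm mean. Against the complete-case t-test, the t-statistic is multiplied by

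k = √{ [n/(n−m)] × [(2n−2)/(2(n−m)−2)] }.

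- m = 1: k = √[(20/19)(38/36)] = 1.054. The critical value 2.024 acts as 2.024/1.054 = 1.921 on 36 df, giving type I error 6.3%.
- m = 2: k = √[(20/18)(38/34)] = 1.114. The critical value acts as 2.024/1.114 = 1.817 on 34 df, giving 7.8%.

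Informative predictors should bring these figures down, and the simulations agree.

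**Step 3, simulated type I error with arm included** (40,000 trials per setting; ranges cover imputation with and without a random residual):

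| Predictors besides arm | 5% missing | 10% missing |
|---|---|---|
| Baseline and an earlier VAS | 5.2–5.8% | 5.3–6.7% |
| Baseline only | 5.7–6.2% | 6.5–7.5% |

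A residual draw does not cure it. With baseline and arm at 10% missing, the range is 6.7–7.5% without a residual and 6.5–7.2% with one. Without a residual, the reported SE over the true SD at 10% missing is 0.93–0.99 (earlier VAS) or 0.91–0.94 (baseline only).

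**Step 4, arm omitted.** Type I error is 4.7–5.3% throughout. With baseline only, the difference shrinks by about the missing fraction f: 1.3 × (1 − f) gives 1.3 × 0.95 = 1.235 and 1.3 × 0.90 = 1.17. Simulated mean estimates of a true 1.3:

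| Predictors | 5% missing | 10% missing |
|---|---|---|
| Earlier VAS already carrying the full effect | 1.27–1.30 | 1.24–1.29 |
| Earlier VAS carrying half the effect | 1.25–1.27 | 1.21–1.24 |
| Baseline only | 1.23–1.24 | 1.16–1.17 |

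In the baseline-only row, power falls from 80% to about 77% at 5% missing and 73–75% at 10%.

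**Step 5, last observation carried forward.** Its type I error is 4.8–5.2%, so it does not share the variance fault. At 10% missing it is nevertheless also significant in 57–90% of the single-imputation false positives, so it flags the fault only in part. If half the effect is present at the earlier visit, it is itself biased, to 1.23–1.24.

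**Step 6, the replacements.** Multiple imputation (20 imputations, Rubin's rules, small-sample df) gives type I error 4.0–5.3% and mean estimates 1.27–1.31. A REML mixed model with three post-baseline visits, unstructured covariance and Kenward-Roger df gives 4.3–5.6%. A model over all visits was not checked.

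**The case against.** The strongest reply is that little VAS should be missing and that imputation would have good predictors. Much of this stands. The run-in aims at "excluding patients who demonstrate poor compliance and are less likely to complete the trial". The closing paragraph of the assessment descriptions lets other assessments be skipped but not the pain VAS. VAS is recorded at every visit from Visit 2 on, so most dropouts will have earlier values. The earlier-VAS rows are therefore the more natural guide, and they show modest distortion. The documents do not specify those predictors, however, so the baseline-only rows cannot be excluded.

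The mixed model might also be fitted to observed data, which would avoid the fault. The text permits that only if the missing-data rule is not taken literally.

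Four stronger readings are tempting but not supported:

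- *Both branches are invalid tests.* With arm omitted, type I error stays near 5%; the cost is bias and power.
- *An average estimate of 1.17 falls below the plan's own threshold.* The 1.3 is the true difference used for sizing, not a cut-off for the estimate. Even an unbiased estimate of a true 1.3 falls below 1.3 about half the time.
- *The sample-size text shows that losses are expected in this trial.* The phrase "Therefore considering dropouts and also to increase the sample in phase I for the clinical outcome" explains the phase 1 increase to 20 subjects. For phase 2, only the Blinding section foresees dropout.
- *Type I error reaches about 15%.* That needs 30% missing with baseline and arm as the only predictors, a rate no figure in the documents supports.

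**Conclusion.** The concern holds, conditionally, and should be fixed. The fault comes from a stated rule, not from a missing detail. At 5–10% missing it is small to moderate: a type I error excess of roughly 0.2 to 2.5 percentage points with arm included, or bias from negligible up to about 10% of the effect with arm omitted. It disappears if no values are missing. The carried-forward sensitivity analysis does not repair the primary analysis. All figures assume values missing completely at random with equal loss per arm; informative or unequal dropout was not quantified.

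**What to change.** Delete single imputation as the intention-to-treat method and pre-specify one replacement.

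1. **Simplest, keeping the t-test:** multiple imputation with arm, randomization stratum, baseline and earlier VAS as predictors, combined by Rubin's rules with small-sample degrees of freedom.
2. **Alternative:** make the planned mixed model primary, fitted by REML to the observed VAS of all randomized subjects without imputation. State the primary time point and the arm contrast at it, a covariance structure that is not overly simple, and small-sample degrees of freedom. A few visits with unstructured covariance and Kenward-Roger is one reasonable choice.

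Last observation carried forward may stay as a sensitivity analysis.

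Option 1 costs SAP wording and modest code; option 2 also changes the primary test. Under multiple imputation, intervals widen by about 1–6% at 5% missing and 2–12% at 10%, against single imputation with the same predictors. Power at 10% missing is about 75–79%, against 80% with complete data. That loss reflects the information not collected.
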